Appendix 2 Study-Specific Visit Windows

Visit	Study Day	Visit Window
Screening	Varies	Before baseline visit (varies)
IV methylprednisolone 1	Varies	Before baseline visit (varies)
IV methylprednisolone 2	At least 1 day after Dose 1	Before baseline visit (varies)
IV methylprednisolone 3 ^a	At least 1 day after Dose 2	Before baseline visit (varies)
Baseline: Rituximab Infusion 1 ^a	1	Within 28 days of screening
Rituximab Infusion 2	8	± 3 days of the targeted date
Rituximab Infusion 3	15	± 3 days of the targeted date
Rituximab Infusion 4	22	± 3 days of the targeted date
Month 1	29	± 3 days of the targeted date
Month 2	60	± 3 days of the targeted date
Month 4	120	± 5 days of the targeted date
Month 6	180	± 5 days of the targeted date
Month 9	270	± 10 days of the targeted date
Month 12	365	± 10 days of the targeted date
Month 15	455	± 10 days of the targeted date
Month 18	545	± 10 days of the targeted date
Every 3 months until the common closeout date	+ 3 months after the last visit	± 10 days of the targeted date
Extended follow-up	+ 3 months after the last visit	± 10 days of the targeted date

IV = intravenous.

^a If clinically indicated and at the discretion of the investigator, additional daily doses (up to three) of IV methylprednisolone can be given. No more than six doses of IV methylprednisolone in total can be given. Each of these additional doses must be given at least 1 day after the previous dose. The final IV methylprednisolone dose and rituximab Infusion 1 can be administered on the same day (although IV methylprednisolone must be given before the rituximab infusion). Rituximab Infusion 1 must occur no later than 14 days after the last IV methylprednisolone dose.

Appendix 3

[Redacted]

[Redacted]

[Redacted]

- [Redacted]
- [Redacted]
- [Redacted]
- [Redacted]

[Redacted]

[Redacted]

Appendix 4 Tanner Stages

Sexual Maturity Stages in Boys and Girls

Stage	Male Genitalia	Pubic Hair	Female Breasts
1	Preadolescent—testes, scrotum, and penis are childlike in size	None; may be vellus hair, as over abdomen	Preadolescent—elevation of papilla only
2	Slight enlargement of scrotum with reddening of skin; little or no enlargement of penis	Sparse growth of long, slightly pigmented, downy hair, straight or slightly curled, primarily at base of penis or along labia	Breast bud stage; breast and papilla form a small mound; areolar diameter enlarge
3	Further enlargement of scrotum; penis enlarges, mainly in length	Hair considerably darker, coarser, and more curled; spreads sparsely over junction of pubes	Further enlargement of breast and areola with no separation of their contours
4	Further enlargement and darkening of scrotum; penis enlarges, especially in breadth; glans develops	Adult-type hair that does not extend onto thighs, covering a smaller area than in adult	Areola and papilla project to form a secondary mound above the contour of the breast; stage 4 development of the areolar mound does not occur in 10% of girls and is slight in 20%; when present, it may persist well into adulthood
5	Adult in size and shape	Adult in quantity and type with extension onto thighs but not up linea alba	Mature female; papilla projects and areola recesses to general contour of breast

Data derived from Tanner JM: Normal growth and techniques of growth assessment. Clin Endocrinol Metab 1986;15:436.

In boys, if different scores are obtained for pubic hair and genitalia, the score for genitalia should be used.

In girls, if different scores are obtained for pubic hair and breast development, the score for breast development should be used.

Appendix 5

EULAR/PRINTO/PRES 2008 Ankara Childhood–Wegener’s Granulomatosis Criteria (with Glossary) and Classification Definition

Histopathology	Granulomatous inflammation within the wall of an artery or in the perivascular or extravascular area
Upper airway involvement	Chronic purulent or bloody nasal discharge or recurrent epistaxis/crusts/granuloma Nasal septum perforation or saddle nose deformity Chronic or recurrent sinus inflammation
Laryngo-tracheo-bronchial involvement	Subglottic, tracheal or bronchial stenoses
Pulmonary involvement	Chest X-ray or CT scan showing the presence of nodules, cavities, or infiltrates
ANCA	ANCA positivity by immunofluorescence or by ELISA (MPO/p or PR3/c ANCA)
Renal involvement	Proteinuria > 0.3 g/24 hr or > 30 mmol/mg of urine albumin/creatinine ratio on a spot morning sample Hematuria or RBC casts: > 5 RBC/high-power field or RBC casts in the urinary sediment or ≥ 2+ on dipstick Necrotizing pauci-immune glomerulonephritis
c-WG EULAR/PRINTO/PRES Ankara 2008 classification definition	At least three of the six following criteria: Histopathology Upper airway involvement Laryngo-tracheo-bronchial stenosis Pulmonary involvement ANCA positivity Renal involvement

ANCA = anti-neutrophil cytoplasmic antibody; CT = computed tomography; c-WG = c-Wegener granulomatosis; ELISA = enzyme linked immunosorbent assay; EULAR = European League Against Rheumatism; MPO = myeloperoxidase; PRES = Pediatric Rheumatology European Society; PR3 = proteinase 3; PRINTO = Pediatric Rheumatology International Trials Organisation; RBC = red blood cell.

Adapted from [Özen et al. 2010](#).

Appendix 6

Chapel Hill Consensus Conference

In 1994, the Chapel Hill International Consensus Conference developed definitions for systemic vasculitides. These definitions are useful in formulating the diagnostic criteria that will be applied to determine a participant's eligibility for this clinical trial with respect to MPA or their exclusion with respect to Churg–Strauss syndrome.

Chapel Hill Consensus Conference Definitions for Microscopic Polyangiitis

- Necrotizing vasculitis with few or no immune deposits affects small vessels (i.e., capillaries, venules, or arterioles)
- Necrotizing arteritis involving small and medium-sized arteries may be present.
- Necrotizing glomerulonephritis is very common.
- Pulmonary capillaritis often occurs.

Chapel Hill Consensus Conference Definitions for Churg–Strauss Syndrome

- Eosinophil-rich and granulomatous inflammation involving the respiratory tract, and necrotizing vasculitis affecting small- to medium-sized vessels, and associated with asthma and eosinophilia

Appendix 7

Procedures for the Intravenous Administration of Rituximab

Rituximab should be given as a slow intravenous (IV) infusion ([Great Ormond Street Hospital 2012](#)). It should not be administered as an IV push or bolus.

Although rituximab may be administered on an outpatient basis, patients may be hospitalized for observation at the discretion of the investigator. Irrespective, rituximab should be administered in a hospital or clinic environment where full resuscitation facilities are immediately available, along with qualified resuscitative personnel and under close supervision of the investigator or designee.

Dosage

The dose of rituximab will be calculated by the physician on the basis of 375 mg/m² of body weight (no maximum dose).

Preparation

Use appropriate aseptic technique. Dilute rituximab to a final concentration of 1 mg/mL to 4 mg/mL in 0.9% NaCl, or 5% Dextrose in Water (USP or British Pharmacopoeia) to a final concentration 1 mg/mL to 4 mg/mL. Gently invert the bag to mix the solution. Do not mix or dilute with other drugs. Discard any unused portion left in the vial. Parenteral drug products should be inspected visually for particulate matter and discoloration prior to administration. No incompatibilities between rituximab and polyvinylchloride or polyethylene bags have been observed.

FOR ALL TREATMENT COURSES THE INFUSION RATES FOR THE FIRST AND SUBSEQUENT INFUSION MUST BE ADHERED TO AS FOLLOWS:

Patients should be medicated pre-infusion with paracetamol/acetaminophen and cetirizine hydrochloride (or similar antihistamine), both according to labelled age-related doses, to be given 1 hour (\pm 15 minutes) before each infusion of rituximab.

First Infusion

Rituximab infusions should commence at a rate of 25 mg/h. This may be escalated at a rate of 25 mg/h increments every 30 minutes to a maximum of 200 mg/h. An example of an infusion schedule is presented below.

Appendix 7 Procedures for the Intravenous Administration of Rituximab (cont.)

Final Concentration = 1 – 4 mg/mL		
Infusion Rate		Minutes
mg/h ^a	mL/h ^a	
25	(.....)	30
50	(.....)	30
75	(.....)	30
100	(.....)	30
125	(.....)	30
150	(.....)	30
175	(.....)	30
200	(.....)	thereafter

^a For countries not able to set the infusion pump to an accuracy of 0.5 mL/h, the rate is to be rounded down to the nearest whole number.

Subsequent Infusions

Patients who have tolerated the first infusion of rituximab well may receive the second infusion. Infusion schedule described for the first infusion should be used also for all subsequent infusions; the infusion rate can be adjusted if the first infusion was well tolerated. Subject to investigator's discretion, corticosteroid premedication with an IV infusion of 100 mg of methylprednisolone may be administered at least 30 minutes prior to the infusion of rituximab (but not prior to clinical assessments) if the patient has experienced an infusion-related reaction with a previous rituximab infusion.

In the event of the patient experiencing an infusion-related reaction during first or any subsequent infusions, the infusion should be stopped immediately. The patient should be clinically assessed and appropriate treatment should be given as per local policy. The principle investigator or sub-investigator(s) should also be informed as soon as possible and all adverse events should be reported as required in Section 5.2. Once the adverse event has resolved, infusion can be restarted at the previous tolerated rate and should be given at the previous reduced rate for 30 minutes. If tolerated, the rate may be increased to the next closest rate on the patient's infusion schedule. Further information is provided in Section 5.2.3.1.

All rituximab infusions should be made through a dedicated line. After the end of each infusion, the IV line should remain in situ for at least 1 hour in order to be able to administer drugs intravenously if necessary. If there are no adverse events during this period of time, the IV line may be removed.

1. BACKGROUND

This document provides specifications for the primary analysis including, remission induction phase, follow-up phase and extended follow-up phase, of the study WA25615.

- **Remission Induction Phase:** Day 1 until end of month 6.
- **Follow-Up Phase:** Post month 6 until common closeout date, where common closeout date is 18 months after the enrolment of the last patient.
- **Extended Follow-Up Phase:** Post common closeout date until CD19 B-cell counts have returned to baseline level or within normal range, whichever is lower.

2. STUDY DESIGN

This is a Phase IIa, international, multicenter, open-label, single-arm study. The primary objectives are to evaluate the safety and tolerability and the PK parameters of rituximab in pediatric patients with severe GPA or MPA.

The study comprises an initial 6-month remission induction phase; rituximab is administered on Days 1, 8, 15 and 22 during this phase. The remission induction phase is followed by a minimum 12-month follow-up phase, after which patients are followed up 3-monthly until the common closeout date, which occurs when the final participant enrolled has completed his or her Month 18 study visit (see [Appendix 2](#)).

Following the remission induction phase (month 6), if required for the maintenance of remission, further courses of rituximab may be given, with the dose and the frequency of retreatment at the discretion of the investigator.

At the common closeout date, patients whose B cells remain depleted and/or have immunoglobulin levels below the LLN for the population, continue to attend study visits every 3 months until their B-cell counts have returned to baseline level or to within the normal range for the population, whichever is lower, and until their immunoglobulin levels have returned to within normal limits for the population. Patients that receive any B-cell therapy or other agent that affects the return of B-cells including but not limited to rituximab, CYC, AZA, on or after the common closeout date, he or she will not be followed any further.

The Study Schema is given in [Appendix 1](#) and the Schedule of Assessments is given in [Appendix 2](#).

2.1 Outcome Measures

This section lists all of the study outcome measures that will be included in this analysis.

2.1.1 Primary Safety Outcome Measures

The primary safety outcome measures are:

- Frequency, nature, and severity of AEs
- Frequency of laboratory abnormalities

2.1.2 Primary Pharmacokinetic Outcome Measures

The primary PK parameters are:

- Clearance (CL) and volume of distribution

2.1.3 Secondary Pharmacokinetic Outcome Measures

The secondary PK parameters of interest are:

- AUC_{0-inf} and C_{max} , derived from the primary PK parameters

2.1.4 Primary and Secondary Efficacy Outcome Measures

None

2.1.5 Secondary Safety Outcome Measures

The secondary safety outcome measures are:

- Vital signs

Rituximab—F. Hoffmann-La Roche Ltd
WA25615: DAP Module 2

[Redacted]

- [Redacted]
 - [Redacted]
 - [Redacted]
 - [Redacted]
 - [Redacted]
 - [Redacted]

- [Redacted]
 - [Redacted]
 - [Redacted]
 - [Redacted]
 - [Redacted]
 - [Redacted]

- [Redacted]
- [Redacted]
- [Redacted]

- [Redacted]
- [Redacted]
- [Redacted]
- [Redacted]
- [Redacted]

- [Redacted]
- [Redacted]
- [Redacted]
- [Redacted]
- [Redacted]
- [Redacted]

2.1.6.2 Exploratory Pharmacodynamic Outcome Measures

[REDACTED]

[REDACTED]

[REDACTED]

[REDACTED]

2.2 Determination of Sample Size

The planned sample size of 25 patients was determined on the basis of the epidemiology of pediatric GPA and MPA plus information from existing patient cohorts. This sample size takes into account the number of pediatric patients that would be eligible for treatment with rituximab and that could be expected to be enrolled within a reasonable timeframe. The primary objective of this study is to evaluate the safety and pharmacokinetics of rituximab in these patients. The planned sample size would be sufficient to provide a reasonable estimate of variability for the mean PK parameters based on the observed intra-patient variability from the RAVE study (a rituximab in ANCA-associated vasculitis trial), protocol number ITN021AI. It would also ensure 95% probability of observing at least one AE when the underlying incidence of that event is $\geq 11\%$.

Given the exploratory nature of this study, there will be no formal statistical hypothesis testing. The study will focus on exploratory estimation of the efficacy and PD endpoints.

2.3 Analysis Timing

There is an interim analysis for this study where the study data for the remission induction phase (6-month time-point) is analyzed when the last patient has reached the 6 month visit and the data have been cleaned with the relevant parts of the database locked for editing.

Primary analysis will be done once all of the data, up until the follow-up visit subsequent to the common closeout date (the Withdrawal visit), has been entered into the study database, cleaned and the database locked for editing.

A final analysis will be reported once the extended follow-up for all appropriate patients has been completed, with all data entered into the database, cleaned and the database fully locked.

2.3.1 Data Included in the Remission Induction Phase

The following data will be included in the analysis of the 6-month time-point:

- **Patients entering the follow-up phase:**
 - All screening and post-baseline data with a clinical date (i.e., administration/assessment/onset/start date) on or before the date of entry into the follow-up phase at Month 6 will be included.

The only exceptions to this is:

- Concomitant medications that begin on the date of entry to the follow-up phase will not be included.
- **Patients not entering the follow-up phase:**

All screening and post-baseline data with a clinical date on or before the date of the patient's last study visit within Study Day 210 will be included; (Day 210 equals 180 days plus a 30-day window).

The data cut will include all data regardless of the type of study visit at which it was collected. This may include data collected at unscheduled visits, dosing termination visits, early termination visits, or safety follow-up visits, if the visit date was on or before the data cutoff date.

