4.3.4 Retreatment with Rituximab

After Month 6, if patients require retreatment with rituximab, further courses will be provided by the Sponsor until the common closeout date. The dose of rituximab and the frequency of retreatment for the maintenance of remission will be at the discretion of the investigator.

Following administration of the first infusion the investigator should review the following safety criteria before administering subsequent infusions of rituximab.

The following are absolute contraindications to receipt of further infusions of rituximab in this study:

- An infusion reaction which necessitated complete discontinuation of the study infusions
- Significant deterioration in patient's general health status since inclusion into the study that results in the patient meeting the exclusion criteria related to General Health
- Emergent primary or secondary immunodeficiency recognized during the study period, including new HIV infection, de novo hepatitis B, hepatitis C, or active tuberculosis infection

Patients who have any of the absolute contraindications to receipt of study infusions with rituximab will be withdrawn from the study and should be encouraged to enter Follow Up.

Patients who develop malignancy during the study will not be able to receive further courses of treatment with the study medication. However, patients with basal cell carcinoma, squamous cell carcinoma of the skin or melanoma in situ (Clarke's Level I), or cervical carcinoma in situ with no stromal invasion (stage 0), which have been completely excised and can be considered as cured, may be retreated with study medication at the discretion of the investigator.

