2.3.2 Data Included in the Follow-up Phase

For patients who enter the Follow-up phase all of their screening data plus post Month-6 data with a clinical date on or before the date of entry into the Extended Follow-up Phase will be included in this analysis of the Follow-up phase.

- **Patients entering the extended follow-up phase:**
All screening and post-Month-6 data with a clinical date on or before the date of entry into the extended follow-up phase will be included.
- **Patients not entering the extended follow-up phase:**
All screening and post-Month-6 data with a clinical date on or before the date of the patient's last study visit within common closeout date will be included.

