
ID: EX001SP
 
Rituximab Treatment Exposure by visit during Remission Induction Phase
	
STREAM Template: None
 
Analysis Population: Safety Evaluable Population
 
Analysis Variables: Number of infusions started, Number infusions completed without them being interrupted/modified, Number of patients with interrupted/modified infusions by infusion number, total dose of RTX. The number of infusions categories need to run from 1 (0 for number completed if necessary) to the maximum number of infusions started.
 
Analysis visits to include are: Baseline, Weeks 1 to 3, Months 1, 2, 4, 6
 
Statistics and Calculation Methods: The Infusion Interrupted/Modified rows count the number of Yes's from the "Was the infusion interrupted/modified" question and the denominator for the %s will be the number of patients who started that infusion number and so will correspond to the appropriate row from "Number of infusions started".
 
Percentages are based on:
 
 1. for "Infusion started" section: based on n 2. for "Infusion Interrupted/Modified" section: based on nn*, where nn* is the number of infusions in corresponding visit.
---	---

```

Rituximab
(N=nn)
-----
Infusions started
n                               nn
Baseline                       nn* (xx.x%)
Week 1                         nn* (xx.x%)
Week 2                         nn* (xx.x%)
Week 3                         nn* (xx.x%)
Month 1                        nn* (xx.x%)
...

Infusion Interrupted/Modified
n                               nn
Baseline                       nn/nn* (xx.x%)
Week 1                         nn/nn* (xx.x%)
Week 2                         nn/nn* (xx.x%)
Week 3                         nn/nn* (xx.x%)
Month 1                        nn/nn* (xx.x%)
...

Total number of infusions completed
n                               nn
0                               nn (xx.x%)
1                               nn (xx.x%)
2                               nn (xx.x%)
...

Total cumulative dose (mg)
n                               nn
Mean (SD)                      xxx.x (xx.x)
Median                          xx.x
Q1 - Q3 (IQR)                  xx.x- xx.x (xx.x)
Min - Max                       xx - xxx

```

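### Under SAP 2.3.1, rituximab retreatment given on the date of entry to follow-up, and reactions starting that date, count as induction-phase data

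*SAP*

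**What the plan says.** **Induction cut (SAP 2.3.1).** For patients entering follow-up, the clinical date is spelled out as the date of administration, assessment, onset or start, and the boundary is inclusive: data with such a date "on or before the date of entry into the follow-up phase at Month 6 will be included". One exception follows: "Concomitant medications that begin on the date of entry to the follow-up phase will not be included". Rituximab is not mentioned in it.

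**Follow-up cut (SAP 2.3.2).** "All screening and post-Month-6 data with a clinical date on or before the date of entry into the extended follow-up phase will be included". Nothing there brings in records dated on the entry day itself.

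**Where retreatment belongs.** SAP section 2 says: "Following the remission induction phase (month 6), if required for the maintenance of remission, further courses of rituximab may be given". Protocol 4.3.4 agrees: "After Month 6, if patients require retreatment with rituximab, further courses will be provided by the Sponsor until the common closeout date". The planned induction infusions are on Days 1, 8, 15 and 22.

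**Phase definition.** SAP section 1 defines induction by time: "Day 1 until end of month 6".

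**Outputs.** EX001SP, the induction exposure table in SAP 5.1, states: "Analysis visits to include are: Baseline, Weeks 1 to 3, Months 1, 2, 4, 6". It also reports the number of infusions completed and the cumulative dose. In SAP section 6, AE001SP, AE002SP and the adverse-event subset tables are produced for induction and overall. AE002.2SP tabulates infusion reactions by infusion number for the same two periods and lists Month 6 among its visits. A reaction is an event during an infusion or in the 24 hours around it that falls in the sponsor's standard term group.

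**The concern.** The date rule and the design description disagree about one day. Both documents treat retreatment as something that follows induction. The cut nevertheless names administration and onset dates and includes the entry date, so an infusion given at that visit becomes a fifth induction infusion.

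The single exception also creates an asymmetry. Protocol 4.4.2.1 lists azathioprine, methotrexate and rituximab side by side as maintenance options after Month 6. Azathioprine recorded as a concomitant medication starting on the entry date is kept out of induction; rituximab given the same day is kept in. A medicine started that day to treat a reaction is excluded, while the reaction is counted.

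Adverse-event frequency is a primary outcome, and the interim analysis in SAP 2.3 reports this phase. With 25 patients, one misattributed patient is visible in a percentage. A reaction can also be divided between phases. Protocol 5.3.5.1 has reactions recorded as separate signs and symptoms, each with its own onset, so symptoms either side of midnight would land in different phases.

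**Working it through.** **1. The section's own figure.** For patients who do not enter follow-up, SAP 2.3.1 cuts at Day 210, explained as 180 + 30 = 210. This reproduces, and it does not bear on the boundary for patients who do enter follow-up.

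**2. The date rules applied to single records.** Assume entry to follow-up on Day 180. Induction takes date ≤ 180 (for concomitant medication, start < 180). Follow-up takes date > 180, reading post-Month-6 strictly.

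| Record | Day | Induction | Follow-up |
|---|---|---|---|
| Fourth planned infusion | 22 | yes | no |
| Retreatment on entry date | 180 | yes | no |
| Reaction with onset on entry date | 180 | yes | no |
| Reaction to that infusion, next day, within 24 h | 181 | no | yes |
| Concomitant medication started on entry date | 180 | no | no |
| Retreatment one day later | 181 | no | yes |

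Rows 2 to 4 are the point. Row 5 shows a related gap: 2.3.1 excludes these medications and, on the strict reading, 2.3.2 does not pick them up.

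**3. Could a Month 6 infusion be one of the planned four?** Protocol 5.2.3.3 allows an infusion to be delayed for infection by at most 14 days. If infusions 2, 3 and 4 were each delayed that long, the fourth would fall at about Day 22 + 3 × 14 = Day 64. The Month 6 analysis window in SAP 3.3 opens at Day 165. Apart from a protocol deviation, an infusion in that window is therefore retreatment. Listing Month 6 in EX001SP and AE002.2SP shows that the SAP allows for infusions around then, but not that they fall on the entry date.

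**4. Size.** Assume 25 patients each complete four induction infusions (4 × 25 = 100) and k of them receive one infusion on the entry date. The documents give no value for k.

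| k (assumed) | Induction infusions, 100 + k | Mean per patient, (100 + k)/25 | Patients with a fifth, k/25 |
|---|---|---|---|
| 0 | 100 | 4.00 | 0% |
| 1 | 101 | 4.04 | 4% |
| 3 | 103 | 4.12 | 12% |
| 5 | 105 | 4.20 | 20% |
| 10 | 110 | 4.40 | 40% |

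For the induction infusion-reaction proportion, a patient adds 1/25 = 4 percentage points only if retreated on the entry date, with a reaction starting that date, and with no earlier induction reaction. The increase therefore lies between 0 and 4k points. For illustration only, two such patients would turn 6/25 = 24% into 8/25 = 32%; with none it stays at 24%.

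**5. Which outputs change.**
- Affected: EX001SP totals and cumulative dose, and the induction versions of AE001SP, AE002SP and the subset tables.
- Largely unaffected: AE002.2SP, because a retreatment reaction has its own infusion column and denominator; VS001SP, because it is restricted to planned infusions; and everything reported overall.

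**The case against.** The strongest reply is that the SAP defines induction by time, and an inclusive boundary is a legitimate choice. EX001SP even lets its infusion categories run up to the maximum number started, so it is not confined to the four planned infusions. This is fair: the documents do not say that the induction tables describe only the four-infusion course. What stands is that the same SAP places retreatment after that phase and never states which phase an entry-day infusion belongs to.

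A reader might infer more than the documents support:

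- **That everything dated on the entry day goes to induction.** It does not; concomitant medications started that day are excepted.
- **That retreatment usually starts at the Month 6 visit.** No document says so. The Month 6 analysis window runs from Day 165 to Day 210, so an infusion labelled Month 6 need not be on the entry date. If none is, the effect is zero.
- **That every retreated patient adds 4 points.** All three conditions in the working must hold. A patient who already reacted during induction adds nothing to a patient-level proportion.
- **That the sponsor recognised the problem for other medicines and missed it for rituximab.** SAP 2.3.1 gives no reason for its exception.
- **That Month 6 should be deleted from EX001SP.** Infusions dated from Day 165 up to the day before entry would be induction data under either rule, and deletion would hide them.

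It is also true that the patient-level exposure listing (EX002SP) and the by-infusion table let a careful reader separate these events, and that no hypothesis test depends on them.

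**Conclusion.** The concern holds for a limited set of outputs. As written, rituximab retreatment given on the follow-up entry date, and adverse events starting that date, count as induction in the pooled induction rows, while a next-day reaction to the same infusion counts as follow-up. This conflicts with SAP section 2 and protocol 4.3.4.

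The number of patients affected is undocumented and may be zero. The effect on the induction infusion-reaction proportion is 4 percentage points for each patient meeting all three conditions, assuming 25 patients in the safety population. The conclusion also rests on reading post-Month-6 in SAP 2.3.2 as after the entry date. On a looser reading the infusion could be claimed by both phases, and clarification would still be needed.

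This is a modest correction to how a primary safety outcome is attributed to phases. It does not affect the overall safety results.

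**What to change.** 1. **SAP 2.3.1:** add a second exception. Rituximab retreatment given on the date of entry to follow-up, and adverse events starting at or after that infusion, including reactions within 24 hours, belong to the follow-up phase. Keep the inclusive boundary for Month 6 assessments, which protocol 4.5 places before any infusion that day.
2. **SAP 2.3.2:** state that these entry-day records are included in follow-up. Without this, the infusion would leave induction and might enter neither phase. The same sentence can settle where entry-day concomitant medications go.
3. **Fallback:** the documents do not show that adverse-event onset time is collected. If it is not, assign same-day events that meet the infusion-reaction definition to the phase of the infusion.
4. **Tables:** keep Month 6 in EX001SP but limit it to infusions dated before the follow-up entry date, and apply the same limit to the induction part of AE002.2SP.

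The cost is a few lines of SAP text and minor extra programming. Linking events to infusions is already required by the 24-hour definition.
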